#### **10.3.1.1.2 Specimen Handling Requirements**

The transmission of infectious agents may occur through contact with contaminated needles and blood or blood products. Consequently, appropriate blood and body fluid precautions should be

employed by all study personnel involved in the collection of blood and handling of specimens in both the clinic and laboratory settings. Refer to current recommendations of the appropriate authorities.

In addition to appropriate handling of subject samples, specific regulations exist regarding the shipment of biologic/etiological samples. Procedures and regulations for the packaging and shipping of infectious samples are outlined in the study laboratory manual or other appropriate reference. The Investigator is responsible for ensuring that all study samples that are to be transported to another location are packed and shipped appropriately according to the applicable regulations.

#### **10.3.1.1.3 Evaluation of Clinical Laboratory Values**

The normal ranges of values for the clinical laboratory assessments in this study will be provided by the responsible laboratory and submitted to VistaGen Therapeutics, Inc. prior to the beginning of the study. They will be regarded as the reference ranges on which decisions will be made.

If a laboratory value is out of the reference range, it is not necessarily clinically relevant. The Investigator must evaluate the out-of-range values and record his or her assessment of the clinical relevance in the appropriate eCRF.

All clinical laboratory values that in the Investigator's opinion show clinically relevant or pathological changes during or after termination of treatment must be reported as AEs and followed, as described in Section [11.2.5](#).

All measurements described in this section are recognized standard methods.

#### **10.3.1.2 Clinical Examinations**

##### **10.3.1.2.1 Vital Signs**

Vital signs, including heart rate, respiratory rate, and seated systolic and diastolic blood pressure will be measured after the subject has been in a seated position for 5 minutes. Temperature will also be measured.

##### **10.3.1.2.2 Twelve-lead Electrocardiogram**

A standard 12-lead ECG will be performed in a supine position after the subject has rested for 5 minutes. All ECG recordings will be identified with the subject number, initials, date, and time of the recording.

All abnormal ECGs will be submitted for a secondary evaluation by a physician with expertise in clinical pharmacology and ECG interpretation. The expert's interpretation will be captured in the EDC system. The external expert will follow-up with the site as needed. Teleconferences can be arranged between the external expert and the site to discuss difficult cases and reach a consensus.

##### **10.3.1.2.3 Physical Examination**

A complete physical examination (excluding the genitourinary examination) will be performed as indicated in the schedule of events ([Table 2-1](#)). The physical examination will include measurement of weight and height, and an examination of the nasal passages.

A focused physical examination will be performed at certain visits as per the schedule of events, but must include examination of the nasal passages and oropharynx; other organ systems should be examined if the subject has symptoms or if the investigator has specific concerns.

#### **10.3.1.2.4 Columbia-Suicide Severity Rating Scale**

The C-SSRS is a semi-structured interview that captures the occurrence, severity, and frequency of suicide-related thoughts and behaviors during the assessment period. The interview includes definitions and suggested questions to solicit the type of information needed to determine if a suicide-related thought or behavior has occurred. The C-SSRS has a “baseline” version which will be completed at Screening and a “Since Last Visit” version that will be completed at all subsequent visits. There are a maximum of 19 items to be completed: 7 that are required, 10 potential additional items if there is a positive response to a required item, and 2 items for suicide/suicide behavior present during the interview. The C-SSRS uses dichotomous scales (i.e., yes or no), Likert scales, and text or narrative to further describe the thoughts or behaviors.

#### **10.3.1.2.5 Penn Physician Withdrawal Checklist**

The PWC-20 is a 20-item simple instrument for assessing anxiolytic discontinuation symptoms. It should be administered by a suitably qualified physician or advanced practice provider.

The PWC-20 consists of 20 questions related to withdrawal from benzodiazepines or other anti-anxiety compounds (see [APPENDIX H](#)). The symptoms measured are based on those that are potentially related to anxiolytic withdrawal: gastrointestinal, mood, sleep, motor, somatic, perception, and cognition. The questions will cover any symptoms that might occur during the week following discontinuation of PH94B.

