## 2.2. Schedule of Events

Table 2-1: Schedule of Events

Assessment/Evaluation	Study Periods					
	Visit 1	Visit 2	Visit 3	Visits 4 to 13	Visit 14 / ET	Visit 15
	Screening	Baseline	1st Month	Monthly	End of Treatment	Follow-up
	[REDACTED]	[REDACTED]	[REDACTED]	[REDACTED]	[REDACTED]	[REDACTED]
Informed Consent Form	X a	X a				
Subject Demographics	X					
Urine Drug Screen	X	X	X	X	X	
Pregnancy Test b	X	X	X	X	X	
MINI 7.0.2	X					
Medical and Psychiatric History	X					
Record Concomitant Medication Use	X	X	X	X	X	
[REDACTED]	[REDACTED]					
LSAS	X	X	X	X	X	
HAM-D17 [REDACTED]						
C-SSRS	X	X	X	X	X	X
Physical Examination c,d	X	X	X	X	X	
Vital Signs	X	X	X	X	X	X
12-Lead Electrocardiogram e	X	X	X	X	X	
Clinical Chemistry, Hematology, and Urinalysis	X	X	X	X	X	
Review Inclusion/Exclusion Criteria	X	X f				
CGI-S	X	X	X	X	X	
CGI-I			X	X	X	
PGI-C			X	X	X	
PWC-20					X	X

Assessment/Evaluation	Study Periods					
	Visit 1	Visit 2	Visit 3	Visits 4 to 13	Visit 14 / ET	Visit 15
	Screening	Baseline	1st Month	Monthly	End of Treatment	Follow-up
	Day -35 to Day -7	Day 0	Day 30 ±3 days	±7 days	52 Weeks ±2 weeks	54 Weeks ±3 days
Training on Use of PH94B		X				
Storage Instructions		X	X	X		
Training on eDiary App to Record PH94B Use and Health Problems		X				
Adverse Event Recording		X	X	X	X	X
Dispense PH94B to Subject		X	X	X		
eDiary Review			X	X	X	

Abbreviations: C-SSRS = Columbia-Suicide Severity Rating Scale; CGI-I = Clinical Global Impression Scale of Improvement; CGI-S = Clinical Global Impression Scale of Severity; eDiary = electronic diary; ET = Early Termination; HAM-A = Hamilton Rating Scale for Anxiety; HAM-D17 = Hamilton Rating Scale for Depression (17 items); LSAS = Liebowitz Social Anxiety Scale; MINI = Mini-International Neuropsychiatric Interview; PGI-C = Patient Global Impression of Change; PWC-20 = Penn Physician Withdrawal Checklist; SAD = social anxiety disorder

- a Subjects will sign an informed consent form for the present study at either Visit 1 or Visit 2, depending on when they enter the study.
- b Pregnancy tests will only be given to female subjects of childbearing potential and not post-menopausal females.

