Subjects will be instructed to return to the clinic for Visit 3 after 30 days ( $\pm 3$  days). At Visit 3, subjects will undergo clinical laboratory assessments (clinical chemistry, hematology, urinalysis, pregnancy test, and urine drug screening), vital signs, 12-lead ECG, physical examination (limited to nasal passage and oropharynx examination unless any AEs are reported), HAM-D17, [REDACTED] LSAS, C-SSRS, CGI-S, CGI-I, and self-evaluation by the patient-reported outcome measure, Patient Global Impression of Change (PGI-C). At Visit 3, PH94B use and any daily reports of health problems that have been recorded in the eDiary application will be reviewed and AEs and concomitant medications will be reported and recorded. Subjects will receive a 1-month supply of PH94B.

Subjects will return to the clinic at monthly intervals ( $\pm 7$  days, Visits 4 to 13), and will repeat the same assessments as those performed at Visit 3. PH94B use and any daily reports of health problems that have been recorded in the eDiary application will be reviewed, AEs and concomitant medications will be reported and recorded at each visit. Subjects will receive a 1-month supply of PH94B at each monthly visit.

At Visit 14 (12 months $\pm$ 2 weeks), treatment will conclude, and subjects will undergo clinical laboratory assessments (clinical chemistry, hematology, urinalysis, pregnancy test, and urine drug screening), vital signs, 12-lead ECG, physical examination, HAM-D17, [REDACTED] LSAS, C-SSRS CGI-S, CGI-I, PGI-C, and the Penn Physician Withdrawal Checklist (PWC-20). Also, PH94B use and any daily reports of health problems that have been recorded in the eDiary application will be reviewed, and AEs and concomitant medications will be recorded and reported. Subjects will also be informed of their follow-up visit (Visit 15).

Subjects will return to the clinic for a follow-up visit (Visit 15, 54 weeks  $\pm$ 3 days), approximately 2 weeks after the last PH94B administration, to undergo C-SSRS, PWC-20, and vital signs assessments, and record AEs.

Subjects who discontinue study treatment without completing 12 months of treatment will attend an Early Termination Visit (Visit 14) as soon as possible after discontinuing treatment, and return to the clinic for a follow-up visit (Visit 15) approximately 2 weeks later.

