#### **13.1.4.5 Penn Physician Withdrawal Checklist**

Descriptive summaries (mean, SD, median, minimum, and maximum) will be presented for scores from the PWC-20 checklist, completed at Visits 14 and 15.

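### For 12-month completers on the nominal schedule, the single PWC-20 reference week has not begun at Visit 14 and closed about 7 days before Visit 15; each rating needs its own stated look-back

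*Protocol*

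**What the plan says.** Protocol 10.3.1.2.5 fixes the reference period of the PWC-20: "The questions will cover any symptoms that might occur during the week following discontinuation of PH94B". SAP 8.7 carries the same sentence. Neither document gives a different period for either visit.

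Protocol 13.1.4.5 plans descriptive summaries of "scores from the PWC-20 checklist, completed at Visits 14 and 15". The schedule of events (Protocol 2.2) shows the checklist at those two visits only. Visit 14 is set at "52 Weeks ±2 weeks" and Visit 15 at "54 Weeks ±3 days".

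Protocol 7.1 says that at Visit 14 "treatment will conclude, and subjects will undergo clinical laboratory assessments", and places Visit 15 "approximately 2 weeks after the last PH94B administration, to undergo C-SSRS, PWC-20, and vital signs assessments, and record AEs". The same section has subjects who stop early attend Visit 14 promptly after stopping, then Visit 15 about two weeks later.

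PWC-20 scores after termination of PH94B are one of eight endpoints mapped to the primary objective (Protocol 6.3). SAP 8.7 restricts the summary to subjects with both visits, does not separate completers from early terminators, and names Visit 1 and Visit 15 as the visits summarised, although the checklist is not given at Visit 1.

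**The concern.** A rating scale needs a look-back that can be applied on the day it is given. The protocol supplies one for its other scales: the past week for LSAS and HAM-D17, one week for CGI, since the last visit for C-SSRS, and comparison with Visit 2 for PGI-C. The PWC-20 has a single period defined by stopping treatment, yet one of its two ratings is made, in completers, on the day treatment ends.

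In a single-arm study the natural reading of a post-treatment withdrawal score is against the same subject's score on drug. The wording does not define Visit 14 as that reference, and for a completer still dosing it asks about days that have not happened. At Visit 15 the days covered depend on whether the instruction is read as written or as an ordinary past-week rating. In early terminators the Visit 14 score is already off drug. The resulting table could not be interpreted without knowing which days each score describes.

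**Working it through.** **Inputs.** Visit 14 at week 52, ±14 days, and Visit 15 at week 54, ±3 days (Protocol 2.2). Stated week = post-dose days 1 to 7 (Protocol 10.3.1.2.5, SAP 8.7). Treatment ends at Visit 14 in completers (Protocol 7.1). The past-week recall used in step 4 is an assumption.

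**1. The plan's own interval.** Visit 14 = 52 × 7 = day 364. Visit 15 = 54 × 7 = day 378. Gap = 378 − 364 = 14 days, which reproduces the protocol's two weeks. With Visit 14 on day 364 and the ±3-day window, Visit 15 falls on post-dose day g = 11 to 17.

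**2. Visit 14, completer dosing up to the visit.** Post-dose days elapsed = 0. None of the 7 stated days exists yet.

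**3. Visit 15, instruction taken as written.** The stated week ended g − 7 days earlier: 14 − 7 = 7 (range 11 − 7 = 4 to 17 − 7 = 10). It can be rated, but only by recall after that delay. Days 8 to g are unrated by this checklist: 7 days (4 to 10).

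**4. Visit 15, taken as a past-week rating.** Days covered are g − 6 to g.

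| Visit 15 on post-dose day | Days covered | Stated days covered | Stated days missed | All off-drug days unrated |
|---|---|---|---|---|
| 11 | 5–11 | 3 | 4 | 4 |
| 14 | 8–14 | 0 | 7 | 7 |
| 17 | 11–17 | 0 | 7 | 10 |

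**5. Off the nominal schedule.** Visit 14 may fall on days 350 to 378 and Visit 15 on days 375 to 381. The gap can therefore run from 375 − 378 = −3 to 381 − 350 = +31 days. With Visit 15 on day 378, a Visit 14 on days 371 to 377 (7 of the 29 allowed days) puts Visit 15 inside post-dose days 1 to 7. Such short gaps satisfy the calendar windows but conflict with the two-week interval in Protocol 7.1.

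**6. Early terminators.** Visit 14 comes after stopping by an unstated number of days and may fall inside days 1 to 7. The SAP's Visit 14 column can therefore contain on-drug and post-stop scores together.

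**The case against.** The strongest reply is that Visit 15 can be carried out exactly as written. The sentence does not say past week; by Visit 15 the first week off drug has fully elapsed, and a rater can ask about it. A reader might infer that the window fits neither rating at all. The documents do not support that, for several reasons:

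- At Visit 15 the stated week can be recalled; the difficulty there is delay and the unrated later days.
- The past-week reading rests on a form that cannot be seen. Appendix H may print its own recall period, and Protocol 10 says raters are trained for consistency.
- Early terminators may be rated inside the stated week at Visit 14.
- Use is as needed and not necessarily daily, so even a completer's last dose may precede Visit 14.
- With the ±3-day window, a past-week recall can overlap the stated week by up to 3 days.

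It might also be inferred that half of the off-drug interval goes unobserved. That is true at most of this checklist: adverse events are still reviewed at Visit 15 and, under SAP 8.1, those between Visits 14 and 15 count as treatment-emergent. Nor do the documents call the PWC-20 the main evidence on withdrawal; the protocol synopsis names adverse events as the primary outcome variable.

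All of this limits the scope. What remains is that the one stated period cannot be applied at Visit 14 to a completer who doses up to that visit, and that no visible text says which days either score should describe.

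**Conclusion.** The point holds for 12-month completers on the nominal schedule. The stated week has not begun at Visit 14 if dosing continued to that visit. At Visit 15 it closed about 7 days earlier (4 to 10), with the same number of later off-drug days unrated by the checklist. If raters use a past-week recall instead, 4 to 7 of the 7 stated days are missed. Separately, the Visit 14 summary can pool on-drug and post-stop scores, because SAP 8.7 does not split by completion status.

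This is a conflict between a stated rule and the visit schedule for an endpoint mapped to the primary objective, so it is more than a missing detail. It limits how PWC-20 scores can be read; it does not leave withdrawal unmonitored. The figures assume a last dose on the day of Visit 14 and Visit 14 on day 364. The past-week figures also assume a recall period that the redacted form may or may not use.

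**What to change.** Replace the sentence in Protocol 10.3.1.2.5 and SAP 8.7 with a look-back for each rating, checked against the Appendix H form:

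- **Visit 14 in completers:** the past week on treatment, labelled as the on-drug reference.
- **Any rating made after stopping:** a stated period that includes the first week after the last dose.
- **Date of discontinuation:** define the date from which it is counted. This matters because use is as needed, and SAP section 10 drops the use-pattern objectives on the ground that eDiary data were unreliable.

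In SAP 8.7, summarise completers and early terminators separately and correct the reference to Visit 1.

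One caution belongs in the text. If Visit 14 looks back 7 days and Visit 15 covers everything since the last dose, nominally 14 days (11 to 17), the second window is 14 / 7 = 2 times as long (11 / 7 = 1.6 to 17 / 7 = 2.4). A longer window gives more opportunity to report symptoms and can raise the Visit 15 score by itself. Where the two look-backs differ in length, the SAP should say so and should not read a rise as withdrawal on that basis alone.

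If ratings have already been made, the SAP should state the recall period actually used.

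The cost is a short wording change in each document, a rater instruction and a split in one table. No visit is added. The downside is a somewhat longer recall at Visit 15.

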#### **10.3.1.3 Adverse Events**

The definitions and management of AEs, and any special considerations for AEs, are provided in Section [11](#).

#### **10.3.2 Efficacy Variables**

##### **10.3.2.1 Liebowitz Social Anxiety Scale**

The LSAS is a clinician-rated scale that has been shown to be sensitive to treatment-related change in social anxiety symptoms. The time frame for rating symptomatology is the past week. The scale consists of 24 items. Each item is given 2 ratings: fear or anxiety on scale of 0 to 3 and avoidance on a scale of 0 to 3, with a total maximum overall score of 144 (see [APPENDIX A](#)). The items in the scale can be divided into performance and social interaction items, and corresponding subscores can be derived.

##### **10.3.2.2 [REDACTED]**

[REDACTED]

[REDACTED]

[REDACTED]

### 10.3.2.3 Hamilton Rating Scale for Depression (17 Items)

The HAM-D17 scale is a 17-item clinician-rated scale to measure the severity of depression, addressing symptoms experienced in the past week, with the total score ranging from 0 to 68 (see [APPENDIX D](#)). A score of 0 to 7 is considered to be within the normal range, while a score of 20 or more indicates at least moderate depression. The time frame for rating symptomatology is the past week.

### 10.3.2.4 Clinical Global Impression Scales

The Clinical Global Impression Scale (CGI) is a clinician-rated scale assessment of the clinician's view of the subject's global health prior to and after participation in a clinical study. The scale assesses the clinician's knowledge of the subject's history, psychosocial circumstances, symptoms, behavior and the effect of these parameters on the subject's capability to function since the last visit with the subject. The CGI consists of 2 components, severity (CGI-S) and improvement (CGI-I). A recall period of 1 week is used.

The severity component (CGI-S) consists of 1 question that assesses the disease severity of the patient population and is on a scale of 1 to 7 ranging from normal (1) to extremely ill (7).

The improvement component (CGI-I) evaluates the change of the subject's condition from the Baseline and is on a scale of 1 to 7 ranging from very much improved (1) to very much worse (7).

In this study the disease severity refers to the severity of SAD. The scale scoring is anchored with reference to the severity of symptoms and functional impairment caused by SAD.

### 10.3.2.5 Patient Global Impression of Change

The Patient Global Impression of Change (PGI-C) is a self-administered instrument that measures change in subjects' overall improvement with treatment on a scale where 1 = "very much improved" and 7 = "very much worse" (see [APPENDIX G](#)). The time frame for rating is compared to the baseline visit (Visit 2).

Very Much Improved	1
Much Improved	2
Minimally Improved	3
No Change	4
Minimally Worse	5
Much Worse	6
Very Much Worse	7

## 11. ADVERSE EVENTS

It is the responsibility of the Investigator at the site to oversee the safety of the study at his/her site. This safety monitoring will include careful assessment and appropriate reporting of SAEs as noted below. Medical monitoring will include a regular assessment of the number and type of SAEs.

The Investigator will record all reportable events with start dates occurring any time after informed consent is obtained until 14 days after the last day of study participation.

### 11.1. Definitions

#### 11.1.1 Adverse Events

An AE is defined as any untoward medical occurrence in a patient or clinical investigation subject administered a pharmaceutical product that does not necessarily have a causal relationship with this treatment. An AE can therefore be any unfavorable and unintended sign (including an abnormal laboratory finding, for example), symptom, or disease temporally associated with the use of a medicinal product, whether or not related to the medicinal product.

Pre-existing diseases or conditions will not be considered AEs unless there is an increase in the frequency or severity, or a change in the quality, of the disease or condition. (Worsening of a preexisting condition is considered an AE.) A pre-existing condition is one that is present at the start of the study. A pre-existing condition should be recorded as an AE if the frequency, intensity, or the character of the condition worsens during the study period (after signing the ICF up to Visit 14 and Visit 15/Follow-up).

For subjects who enter the present study within 14 days of their antecedent PH94B SAD study, AEs ongoing at the time of enrollment into the present study will be recorded in the medical history section of the present study.

Abnormal results of diagnostic procedures are considered to be AEs if the abnormality:

- results in study withdrawal and is associated with an SAE
- is associated with clinical signs or symptoms
- leads to additional treatment or to further diagnostic tests
- is considered by the Investigator to be of clinical significance

In addition, a clinical laboratory abnormality must be documented as an AE if any 1 of the following conditions is met:

- The laboratory abnormality is not otherwise refuted by a repeat test to confirm the abnormality
- The abnormality suggests a disease and/or organ toxicity
- The abnormality is of a degree that requires active management, e.g., change of dose, discontinuation of the drug, more frequent follow-up assessments, further diagnostic investigation, etc.

Pregnancy is not considered an AE, but it is an important medical event, which must be followed up as described in Section 11.3.1.

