**Urinalysis**  
**Macroscopic Panel:** bilirubin, blood, clarity, color, glucose, ketones, leucocyte esterase, nitrite, pH, protein, specific gravity, urobilinogen

**Urine Drug Screen:** If on-site urine drug screen is positive, urine sample will be submitted to central laboratory for confirmatory urine drug screen to be performed:  
opiates, cocaine, amphetamines, barbiturates, benzodiazepines, cannabinoids, methadone, phencyclidine, propoxyphene, methamphetamine, buprenorphine, ecstasy, and oxycodone

**Other:** thyroid stimulating hormone  
free thyroxine (T4) will automatically be performed if thyroid stimulating hormone level is above the upper or below the lower normal limits

The central laboratory should be used for any unscheduled and follow-up labs, if needed. Additional urine and blood samples may be collected for further evaluation of safety as warranted by the Investigator's judgment.

Results and reports from the central laboratory should be filed with the source documents for each subject. The central laboratory will provide laboratory results to the study site as soon as they are available; results will also be provided to the sponsor or designated data manager within agreed upon timelines.

Any laboratory value outside the normal range will be flagged for the attention of the Investigator, who must indicate whether or not the value is of clinical significance. If the result of any laboratory test performed during Screening is clinically significant, the subject should not be advanced to Visit 2 (Baseline) before discussing with the Medical Monitor. However, any abnormal result may be repeated to confirm the finding before excluding the subject from potential inclusion in the study. In addition, subjects should be excluded if they have any other abnormal laboratory test at Screening that, in the Investigator's judgment, is medically significant in that it would impact the safety of the subject, the conduct of the study, or the interpretation of the study results.

Follow-up/unscheduled laboratory tests may be performed on clinically significant abnormalities as indicated by the Investigator. Unscheduled laboratory tests may be repeated at any time at the discretion of the Investigator for appropriate medical care.

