### **13.1.4 Safety and Tolerability Analyses**

Safety analyses will be conducted using data from the safety population (as defined in [Section 13.1.1](#)). Safety variables include treatment-emergent AEs, clinical laboratory values, vital signs, changes in suicidality (C-SSRS), level of depression (HAM-D17), PWC-20 results, ECG readings, and physical examination results. No formal inferential analyses will be conducted for safety variables, unless otherwise noted.

The incidence of AEs for defined periods of exposure (e.g., 3 months, 6 months, 9 months, 12 months, and overall) will be evaluated in the form of a proportion relating number of subjects experiencing events to number of subjects at risk for AEs by organ, relatedness, severity of reported AE, and by frequency of AE. In addition, frequency-type of reported AEs (once, continuous, or adaptability to treatment) by time of occurrence after Visit 2 dispensation may be tabulated. These data will be summarized and tabulated, including CIs when appropriate, for descriptive purposes. Abnormal laboratory values, vital signs, 12-lead ECGs and findings from physical evaluations that are logged as AEs are included.

For each AE category (organ, relatedness, severity, frequency, etc.) the number of subjects reporting 1 or more AEs during the specified time period divided by the number of subjects exposed to the IP during that time period may serve as a nonparametric endpoint, and be subject to evaluation using time series analysis to investigate whether frequency of AEs changes with increased duration of exposure.

Descriptive statistics will be used to portray safety and tolerability of PH94B as measured by reports of AEs and SAEs, changes in laboratory values, 12-lead ECGs, physical examination, vital signs, and withdrawal symptoms.

Safety endpoints are as follows:

- Incidence and severity of AEs, AEs leading to discontinuation, and SAEs
- Changes in vital signs results
- Changes in clinical laboratory evaluation (hematology, chemistry, and urinalysis) results
- Changes in 12-lead ECG results
- Changes in physical examination findings
- Changes in HAM-D17 scores
- Changes in C-SSRS scores
- PWC-20 scores after termination of PH94B

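### Section 11.1.1 makes any new or worsened laboratory abnormality a mandatory AE unless a repeat test refutes it, which conflicts with the Investigator-judgement rule in Section 10.3.1.1.3

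*Protocol*

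**What the plan says.** Protocol Section 11.1.1 has two lists. The first covers abnormal results of diagnostic procedures in general, and one of its triggers is that the abnormality "is considered by the Investigator to be of clinical significance". The second is added for laboratory results: "a clinical laboratory abnormality must be documented as an AE if any 1 of the following conditions is met". Its first condition reads "The laboratory abnormality is not otherwise refuted by a repeat test to confirm the abnormality". The other two are that the abnormality points to disease or organ toxicity, or that it is marked enough to need active management.

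Section 10.3.1.1.3 starts from a different premise: "If a laboratory value is out of the reference range, it is not necessarily clinically relevant". The Investigator must assess each out-of-range value and record the assessment in the eCRF. Values which on that assessment "show clinically relevant or pathological changes during or after termination of treatment must be reported as AEs" are then followed up.

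Section 10.3.1.1.1 has every value outside the normal range flagged, and the Investigator marks whether it is clinically significant. On repeats it says "Follow-up/unscheduled laboratory tests may be performed on clinically significant abnormalities as indicated by the Investigator". The next sentence also leaves unscheduled repeats to the Investigator's discretion.

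Section 13.1.4 settles what enters the AE incidence: "Abnormal laboratory values, vital signs, 12-lead ECGs and findings from physical evaluations that are logged as AEs are included". AE incidence is the first safety endpoint listed there, and the synopsis names AEs as the primary outcome. Sections 8.1 and 8.2 of the SAP give no rule for when a laboratory value becomes an AE.

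**The concern.** The first laboratory condition asks only that no repeat test has refuted the finding. It sets no grade, no size of change and no clinical significance. A value that nobody thinks worth repeating is never refuted, so the least important abnormalities meet the condition most easily. An Investigator's judgement that a value is not relevant then has no effect on whether it must be reported.

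At stake is the study's main result. SAP Section 8.1 counts each subject once, so a single trivial laboratory AE is enough to move a subject into the group with at least one TEAE. The study is open-label with no comparator (Protocol Section 7.2), so there is no concurrent arm against which extra reporting would cancel. Two investigators could each follow a section of the protocol and report different AE rates from identical laboratory data.

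**Working it through.** The plan states no figure on this point, so there is nothing to reproduce. The check is mainly one of logic.

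**1. The two rules applied to one case.** Write N for not refuted, T for suggests disease or toxicity, M for needs active management, and S for judged clinically relevant or significant.

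- Section 11.1.1: AE if N or T or M (or S, through the general list).
- Section 10.3.1.1.3: AE if S.

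Take a new out-of-range value that is judged not relevant, needs no management, suggests no disease and is not repeated. Then N is true and T, M and S are false. Section 11.1.1 makes it a mandatory AE. Section 10.3.1.1.3 does not call for a report. If N were a precondition, so that the rule were N and (T or M or S), both sections would give the same answer.

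**2. What counts as an abnormality.** The term is not defined. Section 10.3.1.1.1 flags every value outside the normal range and treats clinically significant abnormalities as a subset. Exclusion criterion 13 does the same. Section 13.1.4.2 lists out-of-range and clinically significant values separately. No other threshold is given, so the term cannot safely be read as already meaning significant.

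**3. What the rule does not catch.** Sections 11.1.1 and 11.2 treat conditions present at the start or at screening as baseline unless they worsen. The rule therefore applies to new or worsened abnormalities.

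**4. Illustration of scale.** Inputs from the documents:

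- Numeric blood analytes in Section 10.3.1.1.1: 8 hematology + 5 differential + 25 chemistry + TSH = 39.
- Post-baseline panels at Visits 3 to 14 (Table 2-1): 12.
- Results per subject who completes: 39 × 12 = 468.

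Assumed, because the documents do not give it: an out-of-range rate p of 1% to 5% per analyte. Analytes are correlated, so m = 10 effectively independent analytes is shown beside m = 39. The share of subjects with at least one flag at a single visit is 1 − (1 − p)^m.

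| m | p = 1% | p = 5% |
|---|---|---|
| 10 | 1 − 0.99^10 = 9.6% | 1 − 0.95^10 = 40.1% |
| 39 | 1 − 0.99^39 = 32.4% | 1 − 0.95^39 = 86.5% |

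If repeats refuted half of the flags, p is halved. The results become 4.9% and 22.4% for m = 10, and 17.8% and 62.7% for m = 39. None of these figures removes abnormalities already present at baseline.

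**The case against.** The strongest reply is that the bullet is poorly drafted but does limited harm. Several parts of that reply stand.

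- **Not a strict contradiction.** A reader might infer that Section 10.3.1.1.3 says the opposite, so that only relevant values are AEs. It does not. It says that all values judged relevant must be reported, which is a sufficient condition. The conflict is between two working rules.
- **Not every out-of-range value.** A reader might infer this from Section 11.1.1, but the exclusion of pre-existing conditions prevents it.
- **Scheduled panels may count as repeats.** The full panel is taken again each month, and the protocol does not say whether a scheduled test can refute an earlier value. This matters for any cumulative count. At p = 5% with independence, 468 × 0.05 = 23.4 flags per subject. If the next monthly panel can refute a flag, 39 × 11 × 0.05 × 0.05 + 39 × 0.05 = about 3.0 remain. At the other extreme, if flags persisted perfectly, most would already be present at baseline and would not be new AEs. Counts per subject over 12 visits therefore should not be relied on, and subjects are in any case counted once per preferred term.
- **No evidence on site behaviour.** It is tempting to predict many laboratory AEs at some of the roughly 40 sites and almost none at others. The documents do not support this. Every site must record relevance for each out-of-range value, monitors review AE procedures, and the eCRF completion guidelines are not available to check.
- **Descriptive analysis.** No formal safety testing is planned, and tables by preferred term would let laboratory terms be seen separately.

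None of this changes the wording. Because any one condition suffices, the three cannot be read jointly, and a value that is confirmed or never repeated still qualifies whatever the Investigator's judgement.

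**Conclusion.** The point holds as a conflict of operative rules. Read as written, Section 11.1.1 makes any new or worsened laboratory abnormality a mandatory AE if it is merely unrefuted, which leaves the relevance judgement in Section 10.3.1.1.3 with no effect on AE reporting. The SAP does not resolve it. The AE incidence can therefore depend on which section is followed.

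Confidence is high on the wording and low on the size, which cannot be derived from the documents. The single-visit range of about 10% to 40% (10 effective analytes) or 32% to 86% (39 analytes) rests on assumed out-of-range rates and on independence, and it precedes any baseline exclusion. It shows that the effect could be material. It is not an estimate of laboratory AE incidence. The correction should be made.

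**What to change.** Reconcile Sections 11.1.1 and 10.3.1.1.3 by removing non-refutation as a trigger of its own and making it a precondition. In substance: a laboratory abnormality that has not been refuted by a repeat, where one was done, must be documented as an AE if it suggests disease or organ toxicity, or requires active management, or is judged clinically significant by the Investigator under Section 10.3.1.1.3. Say whether the next scheduled panel counts as a repeat. Align the eCRF completion guideline, and state in SAP Section 8.1 which rule the reported AE incidence follows.

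The cost is one sentence in the protocol, a matching line in the guideline and one in the SAP. Fewer laboratory AEs will be logged. No laboratory information is lost, because the shift tables and flagged listings in Protocol Section 13.1.4.2 and SAP Section 8.2 still show every out-of-range value.
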